4.8 Efficacy

The first disease evaluation for subjects following start of olaparib or olaparib in combination with durvalumab will occur at week 8 +/- 7 days. Subsequent to the first tumor evaluation, disease status and tumor response will be assessed per RECIST using standard CT/MRI scans in eight-week intervals (+/- 7 days) until disease progression as defined by RECIST 1.1 or as clinically indicated.

For subjects who discontinue any of the study drug due to toxicity in the absence of confirmed objective progression, objective tumor assessments should be continued every 8 weeks (+/- 7 days) for until confirmed objective disease progression.

If study subject is on durvalumab, disease progression requires confirmation. The confirmatory scan should occur preferably at the next scheduled visit and no earlier than 4 weeks after the initial assessment of progressive disease (PD) in the absence of clinically significant deterioration. Treatment with olaparib and durvalumab will continue between the initial assessment of progression and confirmation for progression. Subjects with rapid tumor progression or with symptomatic progression that requires urgent medical intervention (eg, central nervous system metastasis, respiratory failure due to tumor compression, spinal cord compression) will not be eligible to continue to receive study drug.

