Following randomization, subjects will discontinue platinum chemotherapy and receive either olaparib tablets or olaparib in combination with durvalumab. Study treatment should commence following resolution of chemotherapy toxicities to CTCAE grade 2 or less and no more than 4 weeks after last dose of chemotherapy. Study treatment will continue until disease progression, intolerable toxicity, elective withdrawal from the study, or study completion or termination. Upon treatment discontinuation, subjects will be followed every 2 months for survival.

Safety will be evaluated on an ongoing basis in this study through the monitoring of all serious and non-serious adverse events, graded according to National Cancer Institute Common Terminology Criteria for Adverse Events, Version 4.03 (NCI CTCAEv4.03).

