4.7 Follow-up procedures

30-day safety follow-up

All subjects will have safety evaluations for 30 days following the last dose of the study treatment. AEs will be assessed until 30 days following the last dose of olaparib and/or durvalumab. All concomitant medications given to a patient as a result of an SAE experienced during this period will be recorded. All cancer medications/therapies given to a subject ≤ 30 days after the last dose of olaparib/durvalumab must be recorded. Subjects lost to follow-up should be recorded as such.

Disease progression follow-up

Any subject who has not progressed at the time of discontinuation of study treatment will continue to have tumor assessments performed every 8 weeks (+/- 7 days) until disease progression, initiation of subsequent anticancer therapies or death, whichever comes first.

Survival follow-up

Upon completion of the 30-day safety follow-up or disease progression follow-up, all subjects except those who died, withdrew consent or were lost to follow-up will be followed for survival every 8 weeks (+/- 7 days) until death. Completion of the survival follow-up period will occur once the last subject in the Extension period discontinues study treatment, or the Extension period reaches one year of duration, whichever comes first.

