4.8.1 Efficacy outcome measures

Only response evaluation per RECIST will be entered into eCRF for the Extension period.

The primary efficacy outcome measure is as follows:

PFS, defined as the time from randomization to the first occurrence of disease progression (as determined using RECIST v1.1 criteria and assessed by the Investigator) or death from any cause on study. Death on study is defined as death from any cause within 30 days of the last dose of study treatment regimen. Tumor progression will be assessed locally at each site by the investigators according to RECIST 1.1. No independent review of tumor progression is planned. PFS with disease progression determined by iRECIST will also be examined in exploratory data analysis for the combination arm. The secondary efficacy outcome measures in all subjects are as follows:

- OS (overall survival) defined as the time from randomization until death from any cause.

- ORR (overall response rate) defined as the subjects achieving Complete Response or Partial Response as defined by RECIST 1.1.
- CBR (clinical benefit rate) defined as subjects achieving Complete Response, Partial Response or Stable disease \geq 24 weeks

Methods of measurement

The following definitions and criteria (from RECIST 1.1) should be used for the baseline evaluations of existing disease and for the ongoing evaluation of tumor responses. All measurements should be taken and recorded in metric notation, using a ruler or callipers. In the case of skin lesions, documentation by color photography and a measurement with a ruler to estimate the size of the lesion is recommended.

- **Measurable disease** - the presence of at least one measurable lesion.
- **Measurable lesions** – non-lymph node lesions that can be accurately measured in at least one dimension with LD 20 mm using conventional techniques or 10 mm with spiral CT scan, or 15mm for lymph nodes with spiral CT.
- **Non-measurable lesions** - all other lesions ie, bone lesions, ascites, pleural/pericardial effusion, including lesions that do not meet the measureable criteria above.
- Conventional CT should be performed with cuts of 10 mm or less in slice thickness contiguously. Spiral CT should be performed using a 5-mm contiguous reconstruction algorithm.

All imaging methods should be performed according to institutional standards with each subject having consistency of methods beginning from baseline through the course of the study.

Table 9: Response criteria

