^b Archival tissue (either formalin fixed paraffin embedded tumor specimens or a minimum of 10 unstained paraffin slides) must be available prior to entry into the study. In the absence of archival tissue, fresh tissue biopsy samples, excluding cytology and fine needle aspiration specimens are acceptable.

^c Tumor assessments performed according to RECIST version 1.1 The method used for a patient (CT or MRI) must be the same throughout the study.

^d Tumor assessment performed every 8 weeks starting on Days 21-28 of Cycle 2 and every 8 weeks (+/- 7 days) thereafter until documented disease progression. The results should be reviewed prior to dosing at the next cycle; tumor assessments should be performed <=7 days prior to continuation of study treatment on Day 1 of the subsequent cycle.

^e Includes heart rate, systolic and diastolic blood pressure whilst in a seated position, and temperature. On durvalumab dosing days, recorded prior to dosing and at the end of the infusion.

^f Patients with unresolved adverse events or serious adverse events will be followed until the event is resolved or stabilized, the patient is lost to follow-up or it has been determined that the study treatment or participation is not the cause of the event.

^g Includes RBC count, WBC count, WBC differential count (neutrophils, bands, lymphocytes, eosinophils, basophils, monocytes and other cells), absolute neutrophil count, hemoglobin, hematocrit and platelet count.

^h Includes sodium, potassium, chloride, bicarbonate urea, creatinine, calcium, phosphorus, magnesium, thyroid stimulating hormone (combination arm only), free triiodothyronine (T3) (combination arm only) and free thyroxine (T4) (combination arm only). See Appendix G for additional required tests for Korean sites only.

ⁱ Includes total bilirubin, total protein, albumin, AST, ALT and alkaline phosphatase.

^j As calculated by the Cockcroft-Gault formula.

^k For women of childbearing potential (including those who have had a tubal ligation). For all other women, documentation must be present in medical history confirming the patients is not of childbearing potential.

^l Biomarker blood specimens will be collected at visit C1D1, D1 after each staging cycle (C3D1, C5D1, C7D1 etc), and End of Treatment (EOT).

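### PFS runs from randomization, but scan timing, survival contacts and the PFS death rule hang on dosing, so a subject randomized but never dosed has no clearly stated follow-up path and her progression-free death cannot count

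*Combined protocol and SAP*

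**What the plan says.** **Time origin.** Section 4.8.1 has "PFS, defined as the time from randomization to the first occurrence of disease progression" and "OS (overall survival) defined as the time from randomization until death from any cause". Section 3.8 gives the same origin for PFS and starts OS at entry onto the trial.

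**Scans.** Section 4.8: "The first disease evaluation for subjects following start of olaparib or olaparib in combination with durvalumab will occur at week 8". Appendix A, footnote d, ties the same scan to a treatment cycle: "Tumor assessment performed every 8 weeks starting on Days 21-28 of Cycle 2". After treatment stops, section 4.7 says "Any subject who has not progressed at the time of discontinuation of study treatment will continue to have tumor assessments performed every 8 weeks"; section 4.4 has the same rule.

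**Survival contacts.** Sections 3.1 and 4.4 start them when treatment is discontinued. Section 4.7 starts them later in the sequence: "Upon completion of the 30-day safety follow-up or disease progression follow-up, all subjects except those who died". The 30-day safety period is counted from the last dose.

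**Deaths in PFS.** Sections 3.8 and 4.8.1: "Death on study is defined as death from any cause within 30 days of the last dose of study treatment regimen".

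**Interval before first dose.** Appendix A lists randomization in the screening column, which has a 14-day window. Under section 3.1, platinum stops after randomization, and "Study treatment should commence following resolution of chemotherapy toxicities to CTCAE grade 2 or less and no more than 4 weeks" from the last chemotherapy dose.

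**Analysis.** Section 7.1 tests each arm separately against a median PFS of 2 months. It names no analysis set and no censoring rule.

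**The concern.** The endpoint clock and the follow-up rules have different starting points. A subject who deteriorates, progresses or has unresolved toxicity between randomization and first dose may never receive study drug. She is in the trial for PFS and OS, but she has no drug start, no cycle 2, no treatment to discontinue and no last dose. Two sites could apply the text in good faith and handle her differently.

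The death rule is the sharpest part. Without a last dose, the 30-day condition cannot be met, so a death without documented progression is not a PFS event under the protocol's own definition.

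Non-starters may well be among the earliest failures. Both arms are compared with a fixed historical value, so a selection effect shared by the arms is not cancelled by randomization. If early failures drop out of the analysis, the error favours the drug.

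**Working it through.** **1. The plan's own figure.** Inputs from section 7.1: medians 2 and 4 months, exponential PFS, exponential MLE test, two-sided 5%, power 90%. On the log scale the events needed are ((1.960 + 1.282)/ln 2)² = 21.87, so 22 per arm. The stated 25 subjects follow if 22/25 = 88% have events. Accrual and follow-up times are not stated; 12 months of accrual plus 8 of follow-up, for example, gives 25. The dropout step is 25 × 1.2 = 30. The design figure is reproduced, and this point does not change it.

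**2. The rules set against a never-dosed subject.**

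| Rule | Anchor | Never-dosed subject |
|---|---|---|
| PFS clock (3.8, 4.8.1) | Randomization | Applies |
| First scan (4.8, Appendix A) | Drug start, cycle 2 | No anchor |
| Later scans (4.4, 4.7) | Treatment discontinuation | No clear anchor |
| Survival contacts (3.1, 4.4, 4.7) | Treatment discontinuation, or end of an earlier follow-up phase | No clear anchor |
| Death as PFS event (3.8, 4.8.1) | 30 days from last dose | Cannot be met |

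**3. Size of the bias if early failures are lost.** Assumptions: 30 subjects in the arm, true median 2 months (the null), everyone else followed to an event, and the m earliest failures left out. Censoring at randomization has the same effect, since a time of zero adds neither an event nor follow-up time.

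Let θ0 = 2/ln 2 = 2.885 months and k = 30 − m. The expected estimated median is 2 × (1 + Σ 1/(30 − i + 1)), summed over i = 1 to m:
- m = 1: 2 × (1 + 1/30) = 2.07 months
- m = 2: 2 × (1 + 1/30 + 1/29) = 2.14 months
- m = 3: 2 × (1 + 1/30 + 1/29 + 1/28) = 2.21 months

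The distribution is skewed, so the typical (middle) estimate is slightly lower, as tabulated. Section 7.1 does not say which form of the MLE test is meant, so both are shown:
- Exact: reject upward if 2ΣT/θ0 exceeds the 97.5% point of chi-square on 2k degrees of freedom.
- Log-scale Wald: reject upward if √k × ln(estimate/θ0) exceeds 1.960.

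Simulated upper-tail error under the null:

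| Earliest failures lost | Exact | Log-scale Wald | Typical estimated median (months) |
|---|---|---|---|
| 0 | 2.5% | 1.6% | 1.98 |
| 1 | 3.7% | 2.4% | 2.04 |
| 2 | 5.2% | 3.4% | 2.11 |
| 3 | 7.2% | 4.8% | 2.18 |

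**4. If the non-starters are a random subset.** Losing 1 to 5 of 30 at random leaves the Wald upper-tail error at 1.5–1.6% and the typical median at 1.97–1.98 months. Only precision is lost.

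**The case against.** The strongest reply is that the text is silent on non-starters and does not exclude them. Section 3.1 has 8-weekly tumor measurement on both arms without a dosing condition. Section 4.7 speaks of all subjects, and being never dosed is not among its exceptions. Appendix A, footnote n, sets survival contacts without a dosing trigger. Section 4.4 lets the end-of-treatment visit run from a decision to stop the drug. Section 4.1.5 allows a scan whenever progression is suspected, and progression found that way is a PFS event. This stands: a reader might infer that never-dosed subjects are not followed, and the documents do not go that far. But section 3.1 gives no start point, section 4.7 still requires an earlier phase to be completed, and none of these passages repairs the death rule.

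A reader might also infer that PFS is inflated as planned. That does not follow either. Leaving subjects out or censoring them at randomization is an assumption, since section 7.1 is silent, and the bias also needs non-starters to be early failures.

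Larger figures are tempting. Under the null, a 2-week gap contains 1 − 2^(−0.46/2) = 14.7% of PFS events, or 4.4 of 30; losing all of them would give 9.8% (exact) or 6.5% (Wald). But silent progression would not stop a subject from starting drug, so most of these subjects would be scanned at week 8 and counted.

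Two further inferences are weak. OS has no last-dose condition, so it is less affected. The comparison between arms is exploratory, so harm to it is not harm to the primary test.

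Finally, the current text has reduced data collection for an Extension period, which suggests, without proving it, that accrual may be over. New scan wording might then recover little. The analysis set and the death rule could still be settled.

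**Conclusion.** The point holds as a gap in the follow-up text together with a death rule that gives the wrong answer for one class of subject. A randomized, never-dosed subject has no clearly stated follow-up path, and her progression-free death cannot be a PFS event.

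The effect on the primary test is conditional. With 1 to 3 early failures lost per arm of 30, the upper-tail error is 3.7–7.2% (exact) or 2.4–4.8% (Wald), and the typical estimated median moves from 1.98 to 2.04–2.18 months. With three lost, the error is about three times its baseline under either test; with one lost, the Wald version stays inside the nominal 2.5%. The shift in the median is small beside the 2-month improvement sought.

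These figures assume exponential PFS, complete follow-up of all others, and omission or censoring at randomization of the earliest failures. The number of non-starters is not given, so 1 to 3 is an assumption. There is no bias if non-starters are a random subset and no harm if every subject starts. The correction is worth making because it is cheap and protects the primary endpoint.

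**What to change.** - In section 7.1, state that PFS and OS are analysed in all randomized subjects, and give the censoring rule for subjects without an event.
- In sections 3.8 and 4.8.1, count a death in a never-dosed, progression-free subject as a PFS event without reference to a last dose.
- In sections 4.4, 4.7 and 4.8 and Appendix A, state that 8-weekly tumor assessments counted from randomization, and survival contacts, apply to every randomized subject whether or not dosed.

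The sample size stays at 25 per arm, inflated to 30. The cost is wording, follow-up of probably a few subjects, and a PFS estimate that may be slightly less favourable.

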4.8.1 Efficacy outcome measures

Only response evaluation per RECIST will be entered into eCRF for the Extension period.

The primary efficacy outcome measure is as follows:

PFS, defined as the time from randomization to the first occurrence of disease progression (as determined using RECIST v1.1 criteria and assessed by the Investigator) or death from any cause on study. Death on study is defined as death from any cause within 30 days of the last dose of study treatment regimen. Tumor progression will be assessed locally at each site by the investigators according to RECIST 1.1. No independent review of tumor progression is planned. PFS with disease progression determined by iRECIST will also be examined in exploratory data analysis for the combination arm. The secondary efficacy outcome measures in all subjects are as follows:

- OS (overall survival) defined as the time from randomization until death from any cause.

- ORR (overall response rate) defined as the subjects achieving Complete Response or Partial Response as defined by RECIST 1.1.
- CBR (clinical benefit rate) defined as subjects achieving Complete Response, Partial Response or Stable disease \geq 24 weeks

Methods of measurement

The following definitions and criteria (from RECIST 1.1) should be used for the baseline evaluations of existing disease and for the ongoing evaluation of tumor responses. All measurements should be taken and recorded in metric notation, using a ruler or callipers. In the case of skin lesions, documentation by color photography and a measurement with a ruler to estimate the size of the lesion is recommended.

- **Measurable disease** - the presence of at least one measurable lesion.
- **Measurable lesions** – non-lymph node lesions that can be accurately measured in at least one dimension with LD 20 mm using conventional techniques or 10 mm with spiral CT scan, or 15mm for lymph nodes with spiral CT.
- **Non-measurable lesions** - all other lesions ie, bone lesions, ascites, pleural/pericardial effusion, including lesions that do not meet the measureable criteria above.
- Conventional CT should be performed with cuts of 10 mm or less in slice thickness contiguously. Spiral CT should be performed using a 5-mm contiguous reconstruction algorithm.

All imaging methods should be performed according to institutional standards with each subject having consistency of methods beginning from baseline through the course of the study.

Table 9: Response criteria

Evaluation of target lesions	
Complete Response (CR):	Disappearance of all target lesions
Partial Response (PR):	At least 30% decrease in the sum of the LD of target lesions, taking as reference the baseline sum LD
Progressive Disease (PD):	At least a 20% increase in the sum of the LD of target lesions, taking as reference the nadir (smallest sum) LD recorded since the treatment started or the appearance of one or more new lesions
Stable Disease (SD)	Neither sufficient shrinkage to qualify for PR nor sufficient increase to qualify for PD, taking as reference the smallest sum LD since the treatment started
Evaluation of non-target lesions	
Complete Response (CR):	Disappearance of all target lesions
Stable Disease (SD)	Persistence of one or more non-target lesion(s)

Progressive Disease (PD):	Appearance of one or more new lesions and/or unequivocal progression of existing non-target lesions
---------------------------	---

Evaluation of Best Overall Response

The best overall response is the best response recorded from the start of the treatment until disease progression and is determined as per Table 10 below.

Table 10: Definition of best overall response as per RECIST criteria

Target lesions	Non-Target lesions	Evaluation of New lesions	Overall response
CR	CR	No	CR
CR	SD	No	PR
PR	Non-PD	No	PR
SD	Non-PD	No	SD
PD	Any	Yes or No	PD
Any	PD	Yes or No	PD
Any	Any	Yes	PD

To be considered a response, CR or PR must persist for a minimum of 4 weeks. If, at the time of tumor response evaluation, either a PR or CR is observed, the same radiographic study should be repeated 4 weeks later for confirmation of response. After this confirmatory study, subjects should return to the schedule of evaluations as previously described.

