4.4 Procedures for discontinuation of a subject from investigational product

A subject whose treatment is permanently discontinued due to an adverse event or clinically significant laboratory value must be followed up as per institutional practice until resolution or stabilization of the event, whichever comes first.

An end of treatment (EOT) visit should be conducted within 30 days of the last dose of the study drug or within 30 days of the decision to permanently discontinue the study drug. If the subject withdraws from the study at a scheduled visit, the EOT assessment can be performed on that day. (See section 4.5.3 for visit details)

Any subject who has not progressed at the time of discontinuation of study treatment will continue to have tumor assessments performed every 8 weeks until disease progression, initiation of subsequent anticancer therapies or death, whichever comes first.

Upon treatment discontinuation, subjects will be followed every 2 months for survival. Completion of the survival follow-up period will occur once the last subject in the Extension period discontinues study treatment, or the Extension period reaches one year of duration, whichever comes first.

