7 STATISTICAL METHODS AND SAMPLE SIZE DETERMINATION

7.1 Statistical analyses and determination of sample size

Based upon current standard of care,³⁰ the median PFS (mPFS) in this population is estimated to be approximately 2 months, and a clinically relevant improvement with either of the proposed maintenance treatments would be to an mPFS of 4 months. In both arms of the study, it is proposed to test a null hypothesis of an mPFS of 2 months against an alternative hypothesis of an mPFS of 4 months. To test this hypothesis, assuming an exponential PFS distribution, use of an exponential MLE test, a two-sided significance level of 5% and a power of 90%, 25 subjects are required per arm. To allow for a drop-out rate of approximately 20%, the sample size per arm will be inflated to 30 subjects, for a total of 60 subjects.

Comparison between the two treatment arms will be performed as an exploratory analysis.

The number of subjects that will agree to participate in the genetic research is unknown. It is therefore not possible to establish whether sufficient data will be collected to allow a formal statistical evaluation or whether only descriptive statistics will be generated. A statistical analysis plan will be prepared where appropriate.

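### The primary PFS endpoint excludes deaths more than 30 days after the last dose, even without prior progression, and this generally favours each arm

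*Combined protocol and SAP*

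**What the plan says.** Sections 3.8 and 4.8.1 define PFS as time from randomization to investigator-assessed RECIST 1.1 progression or death on study. Both then narrow the second component in the same words: "Death on study is defined as death from any cause within 30 days of the last dose of study treatment regimen".

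Follow-up does not end at that point. Section 4.4 states: "Any subject who has not progressed at the time of discontinuation of study treatment will continue to have tumor assessments performed every 8 weeks". Section 4.7 gives the end of those assessments as "until disease progression, initiation of subsequent anticancer therapies or death, whichever comes first", after which subjects "will be followed for survival every 8 weeks (+/- 7 days) until death", subject to an overall cut-off tied to the Extension period. For subjects who discontinue any study drug because of toxicity, Section 4.8 says "objective tumor assessments should be continued every 8 weeks (+/- 7 days) for until confirmed objective disease progression", and it names no stop at new therapy.

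The secondary survival endpoint has no such window: "OS (overall survival) defined as the time from randomization until death from any cause".

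Section 7.1 sets the test, separately in each arm: "it is proposed to test a null hypothesis of an mPFS of 2 months against an alternative hypothesis of an mPFS of 4 months". It specifies an exponential MLE test, two-sided 5%, 90% power and 25 subjects per arm, raised to 30 for drop-out. It gives no censoring rules.

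**The concern.** Take a subject who stops treatment without progression, lives past day 30 and dies before a scan shows progression. The trial records the death, but the primary endpoint has neither a progression nor a death for this subject. Nothing in the supplied text brings the death back into PFS. Nothing says when this subject is censored, or when a subject who starts new therapy before progression is censored.

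Removing a death from the event count while keeping nearly all of the follow-up time makes PFS look longer. In a two-arm comparison part of this might cancel. Here the between-arm comparison is exploratory and each arm faces a fixed 2-month benchmark, so the shift acts directly on the primary test. The 30-day window is also undefined for a randomized subject who never received a dose.

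**Working it through.** **The plan's own figure.** On the log scale the required events are ((1.960 + 1.282)/ln 2)² = 21.87. Section 7.1 gives no follow-up time. Assuming 12 months, the chance of an event at a 4-month median is 1 − 2^(−12/4) = 0.875, and 21.87/0.875 = 24.99, so 25. Then 25 × 1.2 = 30. The sample size is not in dispute.

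**Direction.** Let an arm have n subjects, all with events, and total time S, so the estimated mean PFS is S/n. Lose one death and censor that subject g days before it. The estimate becomes (S − g)/(n − 1), which exceeds S/n exactly when g < S/n. At a 2-month median the mean is 2/ln 2 = 2.885 months = 88 days. On-schedule scans are at most 56 + 7 + 7 = 70 days apart, so the usual shift is upward. Scans stop at new therapy, however, so longer gaps can occur and can reverse it.

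**Size.** Assumptions: true median 2 months, n = 25 or 30, and k = 1, 2 or 3 lost deaths (not given in the documents). Two censoring rules bracket the on-schedule case:

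- Time kept to death: d = n − k events, and the estimate is multiplied by n/(n − k). Because 2S·(ln 2)/2 follows a chi-square with 2n degrees of freedom, the exact favourable-tail error is P(χ²₂ₙ > χ²₀.₉₇₅,₂d). For n = 25 and k = 0, P(χ²₅₀ > 71.42) = 2.50%. For k = 1, P(χ²₅₀ > 69.02) = 3.85%.
- Censoring at the last 56-day scan: 300,000 simulated arms, with lost deaths drawn from event times over 30 days.

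| n | k | Median ratio, last scan | Median ratio, to death | Exact error, last scan | Exact error, to death |
|---|---|---|---|---|---|
| 25 | 1 | 1.027 | 1.042 | 3.4% | 3.9% |
| 25 | 2 | 1.057 | 1.087 | 4.7% | 5.8% |
| 25 | 3 | 1.089 | 1.136 | 6.3% | 8.5% |
| 30 | 1 | 1.023 | 1.034 | 3.3% | 3.7% |
| 30 | 2 | 1.047 | 1.071 | 4.4% | 5.4% |
| 30 | 3 | 1.073 | 1.111 | 5.7% | 7.7% |

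On a 2-month median this is about 1-3, 3-5 and 4-8 days for one, two and three lost deaths. With last-scan censoring the estimate fell in at most 0.2% of arms.

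**Version of the test.** Section 7.1 does not say which form of the exponential MLE test is meant, and the error depends on it. Ranges cover both sample sizes and both censoring rules:

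| Test | k = 0 | k = 1 | k = 2 | k = 3 |
|---|---|---|---|---|
| Exact chi-square | 2.5% | 3.3-3.9% | 4.4-5.8% | 5.7-8.5% |
| Log-scale Wald | 1.5-1.6% | 2.1-2.4% | 2.9-3.7% | 3.8-5.6% |
| Hazard-scale Wald | 3.4-3.5% | 4.4-5.3% | 5.8-7.8% | 7.5-11.2% |
| Mean-scale Wald | 0.3-0.4% | 0.4-0.6% | 0.5-0.9% | 0.8-1.4% |

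**When it does not bias upward.** With censoring two scans earlier, the estimate fell in 53-59% of arms, the mean change was −0.3% to −1.2%, and the exact error stayed at 2.5-2.6%. About 79% of those lost deaths are then censored at day 0, so this case shows that reversal is possible rather than how often it would happen.

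**A second parameterisation.** This uses 25 per arm, 12 months of follow-up and a log-scale Wald test, with 5%, 10% or 20% of first PFS events after month 2 taken as late deaths. The error is 1.2-1.7% with all deaths counted. Under the 30-day rule it is 2.1%, 3.1% and 5.7% if those subjects are censored at death, and 2.2%, 2.5% and 4.5% if censored at a scan up to 63 days earlier.

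**The case against.** The strongest reply is that few subjects will be affected. Treatment normally runs to progression, and scans continue after stopping. A lost death requires stopping without progression, surviving 30 days and dying before the next positive scan. With one such death the median moves by 1 to 3 days, and the log-scale and mean-scale tests remain below 2.5%. The largest errors combine the worst count, censoring rule and test. A Kaplan-Meier median would often not move: with one lost death it was unchanged in 69-86% of simulated arms, a share that depends on the convention for the median. All of this stands, and it limits the size.

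The simulation also measures 30 days from randomization rather than from the last dose, and treats all 30 subjects as complete. These are approximations.

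A further point is timing. This version already covers the Extension period, and under Section 7.2 the Study Chairs see accruing deaths and progressions. A late change to the primary endpoint invites suspicion. That calls for documentation and a fallback, but it does not make the present definition sound. The window matches the protocol's 30-day safety period, but a safety-reporting window is not a reason to drop deaths from an efficacy endpoint. Some front pages are absent from the supplied copy, so a censoring rule there cannot be excluded. The two operative definitions are present and agree.

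**Conclusion.** The concern holds and should be fixed. A stated rule, given twice, removes observed deaths without documented progression from the primary endpoint. Under on-schedule censoring, or with time kept to death, it raises the estimated median by about 2-4%, 5-9% and 7-14% for one, two and three lost deaths per arm. The exact favourable-tail error rises from 2.5% to at most 3.9%, 5.8% and 8.5%. These figures rest on an exponential distribution with a true 2-month median and on assumed counts. If no such deaths occur there is no bias. If censoring precedes the death by more than the arm's estimated mean PFS, the estimate falls. Direction and size thus depend on a censoring date that the supplied text does not give.

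**What to change.** In Sections 3.8 and 4.8.1:

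- Define a PFS event as first RECIST 1.1 progression, or death from any cause without prior progression, whatever the time since the last dose. This also covers subjects who were never dosed.
- Censor subjects alive without progression at their last adequate tumor assessment.
- State one rule for new anticancer therapy before progression. Censoring at the last assessment before that therapy is one option. It leaves deaths after new therapy uncounted, so the alternative should be reported as a sensitivity analysis.
- Keep the 30-day version, and censoring of deaths after two or more missed scans, as sensitivity analyses.

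In Section 7.1, name the version of the exponential MLE test. Record when and why the change was made, and that accrued results did not prompt it. If the primary definition can no longer change, pre-specify the all-deaths version as a sensitivity analysis and report both.

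The cost is a documented change to the primary endpoint definition. No visits or scans are added, because survival and subsequent therapies are already collected about every 8 weeks (Appendix A, footnote n). The sponsor should confirm that death and new-therapy dates still reach the database, since Section 4.8.1 also says "Only response evaluation per RECIST will be entered into eCRF for the Extension period". Estimated PFS may be slightly shorter, and some deaths after a gap without scans will count as events. The new-therapy rule and the missed-scan analysis address the latter.
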